5.1.2.3 Management Guidelines

Dermatologic Reactions

Investigators should remain vigilant for dermatologic signs or symptoms at scheduled study visits. Symptomatic relief of dermatologic manifestations can include topical emollients for mild to moderate skin effects and topical corticosteroids and/or oral antihistamines for more severe skin effects. Inability to achieve symptomatic relief may require local dermatologic assessment for further evaluation, including recommended biopsy and management.

Guidelines for the management of patients who develop dermatologic reactions are provided in [Table 4](#).

Infusion-Related Reactions

All infusions will be administered in the clinic to enable monitoring for possible infusion-related reactions. Patients must be monitored for approximately 30 minutes after each study drug infusion. Medicinal products for the treatment of severe reactions (e.g., epinephrine, antihistamines, and glucocorticoids) must be available for immediate use in the clinic. Resuscitation equipment should also be available.

Infusion-related reactions may include both acute allergic/hypersensitivity (e.g., anaphylactic) reactions and acute pseudoallergic/hypersensitivity-like (e.g., anaphylactoid) reactions. These may have similar clinical manifestations, but they have different mechanisms (e.g., only allergic reactions are IgE-mediated) and risks of re-challenge. Differentiating allergic reactions from pseudoallergic reactions is important because it may impact the understanding of the risk profile of the drug. In instances where the reaction occurs with the first infusion of the study drug without any suspicion of prior sensitization, it is less likely to be an allergic reaction. When a new reaction is seen with the second or subsequent infusions, or if there is an atypical presentation (e.g., rapid onset within 15 minutes or increase in severity when compared with previous reactions), there is a higher likelihood that the reaction is allergic. Investigators should report infusion-related reactions using the most appropriate term, based on their medical judgment. The investigator should also discuss with the Medical Monitor the possibility

of obtaining additional supportive data, if available, to inform the diagnosis of allergic versus pseudoallergic reaction (e.g., serum histamine, serial tryptase measurements).

Patients should be instructed to recognize the symptoms of a severe allergic (e.g., anaphylactic) or pseudoallergic (e.g., anaphylactoid) reaction and to contact a healthcare provider or seek immediate care in case of any such symptoms. Patients are to be provided with alert cards to remind them and a caregiver or partner of these instructions.

Guidelines for the management of patients who develop infusion-related reactions are provided in [Table 4](#).

Epithelial Tumors

Investigators should remain vigilant for signs or symptoms of cancer in scheduled study visits. Any signs or symptoms that could be suggestive of malignancy should be promptly and aggressively evaluated and reported to the Sponsor. If a patient develops epithelial tumors (as defined in [Table 4](#)) during the study, study drug must be discontinued permanently. In cases of newly diagnosed malignancy or epithelial high grade dysplasia, unstained slides and/or representative tissue blocks may be requested by the Sponsor for further evaluation and characterization.

Guidelines for the management of patients who develop epithelial tumors are provided in [Table 4](#).

Serious Infections

To assess for the potential development of an immune response, including neutralizing ADAs against endogenous IL-22, antibody samples will be obtained at baseline (Study Week 0), at regular intervals during treatment, and during the safety follow-up period and stored appropriately for further evaluation as needed.

Guidelines for the management of patients who develop infections are provided in [Table 4](#).

Hepatic Events

If treatment-emergent ALT or AST elevations are observed, ALT, AST, alkaline phosphatase, and total bilirubin tests (i.e. liver function tests [LFTs]) should be repeated within 48–72 hours to confirm the abnormality and to determine whether transaminases are increasing or decreasing.

For re-testing done locally or at a central laboratory facility, normal laboratory ranges should be recorded, results should be made available to trial investigators immediately, and the data should be included in the eCRF.

If treatment-emergent ALT or AST elevations are confirmed, other laboratory tests should be performed to rule out acute viral hepatitis (i.e., hepatitis A, B, C, D, or E),

autoimmune hepatitis (i.e., anti-nuclear antibody, anti-smooth muscle antibody, anti-mitochondrial antibody, or anti-LKM-1 antibody), or functional hepatic impairment (i.e., INR or fractionated bilirubin). Further LFT monitoring to ensure patient safety should be performed on the basis of clinical judgment and local practice. Imaging tests and hepatology consultation should be considered. In addition, a more detailed history of the event should be obtained, including the following: symptoms, prior or current diseases, concomitant drug use (including nonprescription medications and herbal and dietary supplements), alcohol use, recreational drug use, and special diets.

Regarding re-initiation of study drug, the benefit-risk assessment takes alternate causes (e.g., acute viral hepatitis, newly initiated concomitant medication, treated gallstone disease) and reversibility into consideration, but the recommendations for a specific patient are complex and require medical judgment (i.e., consultation between the investigator, medical monitor, and the IMC). In general, re-initiation of study drug can be considered if there is clear evidence that the liver injury is not related to study drug or clearly attributable to other causes (as determined by the IMC), is showing signs of reversibility, and that the benefit-risk of continuing to receive study drug remains favorable. Because establishing a diagnosis of drug-induced liver injury is frequently challenging, the IMC may involve outside hepatology experts or consultants as necessary. If the study drug is re-initiated, there remains a potential risk of recurrence of liver injury due to the possibility of an erroneous causality assessment. Hence, patients will need to be monitored carefully after re-initiation of study drug. If LFTs worsen significantly after re-initiation, study drug should be permanently discontinued.

Guidelines for the management of patients who develop treatment-emergent ALT or AST elevations are provided in [Table 4](#). For patients with suspected or confirmed severe liver injury as defined by Hy's Law, refer to Section [5.3.5.7](#).

Thromboembolism or Deep Vein Thrombosis

Investigators should remain vigilant for signs and symptoms suggestive of thromboembolism or deep vein thrombosis in scheduled study visits. Any signs or symptoms that could be suggestive of thromboembolism or deep vein thrombosis should be promptly and aggressively evaluated and reported in an expedited manner to the Sponsor (see Section [5.2.3](#)). Guidelines for the management of patients who develop Grade ≥ 2 thromboembolism or deep vein thrombosis are provided in [Table 4](#).

Table 4 Guidelines for Management of Patients Who Experience Specific Adverse Events

Event	Action to Be Taken
Dermatologic adverse event	
Grade 1 or 2	
 Continue study drug. Treat with topical emollients.
Grade 3	
 Withhold study drug. Treat with topical emollients and with topical corticosteroids and/or oral antihistamines. If no symptomatic relief, refer patient to dermatologist for further assessment and treatment. If treatment with oral immunosuppressants is required, discontinue study drug. If event resolves to Grade 2 or better with topical treatment, resume study drug at the next scheduled dose. If more than one scheduled dose will be missed because of an on-going adverse event, permanently discontinue study drug.
Grade 4	
 Permanently discontinue study drug. Refer patient to dermatologist for assessment and treatment.
Infusion-related reactions	
Grade 1 or 2	
 Reduce infusion rate to \leq50% of original infusion rate. Interrupt infusion if symptoms persist. Provide supportive treatment if indicated. If infusion was interrupted, resume infusion at 50% of original infusion rate upon symptom resolution. If infusion reaction reoccurs, discuss with Medical Monitor before premedicating with acetaminophen or diphenhydramine at subsequent infusions.
Grade 3 and 4	
 Stop infusion immediately and administer supportive treatment as per local or institutional standard operating procedures (see Appendix 9 for guidance on anaphylaxis). Permanently discontinue study drug. Discuss with Medical Monitor the possibility of obtaining additional supportive data, if available, to inform the diagnosis of allergic versus pseudoallergic reaction (e.g., serum histamine, serial tryptase measurements).

ADA=anti-drug antibody; AESI=adverse event of special interest; LFT=liver function test; PK=pharmacokinetic; ULN=upper limit of normal.

Table 4 Guidelines for Management of Patients Who Experience Specific Adverse Events (cont.)

Event	Action to Be Taken
Infection	
Grade 1 or 2	
 Continue study drug.
Grade 3	
 Withhold study drug. Collect PK and ADA sample if not collected at study visit, and treat according to local standards. If the infection is clearly not study-drug related (i.e., there is a clear alternative explanation for the infection), the infection and symptoms are fully resolved at least 1 week prior to the next scheduled dose, and any treatment for the infection has been completed at least 1 week prior to the next scheduled dose, consult the Medical Monitor to determine if study drug can be resumed. If these conditions are not met or the Medical Monitor indicates that study drug should not be resumed, permanently discontinue study drug.
Grade 4	
 Permanently discontinue study drug. Collect PK and ADA sample if not collected at study visit, and treat according to local standards.
Suspected or confirmed COVID-19 infection	
Grades 1–3	
 Withhold study drug If the infection and symptoms are fully resolved at least 1 week prior to the next scheduled dose, and any treatment for the infection has been completed at least 1 week prior to the next scheduled dose, consult the Medical Monitor to determine if study drug can be resumed. If these conditions are not met or the Medical Monitor indicates that study drug should not be resumed, permanently discontinue study drug.
Grade 4	
 Permanently discontinue study drug.
Epithelial tumor	
New malignancy, unresectable colonic mucosal dysplasia, or any high-grade colonic mucosal dysplasia	
 Permanently discontinue study drug.
New cervical intraepithelial neoplasia of Grade >1, cervical smear indicating the presence of adenocarcinoma in situ, or high-grade squamous intraepithelial lesion	
 Permanently discontinue study drug.

ADA=anti-drug antibody; AESI=adverse event of special interest; LFT=liver function test; PK=pharmacokinetic; ULN=upper limit of normal.

Table 4 Guidelines for Management of Patients Who Experience Specific Adverse Events (cont.)

Event	Action to Be Taken
Hepatic event	
ALT or AST $>3 \times$ ULN to $\leq 5 \times$ ULN	
 Continue study drug. Repeat LFTs within 48-72 hours. If LFT results confirmed, test for alternative cause(s) as described in Section 5.1.2.3.
ALT or AST $>5 \times$ ULN to $\leq 8 \times$ ULN	
 Withhold study drug. Repeat LFTs within 48-72 hours. If LFTs confirmed, test for alternative cause(s) as described in Section 5.1.2.3. Monitor LFTs weekly until AST and ALT $\leq 5 \times$ ULN. If event resolves to AST or ALT $\leq 5 \times$ ULN within 2 weeks after event onset, resume study drug. If not, monitor as described in the next category.
Any one of the following: 
 ALT or AST elevation $>8 \times$ ULN ALT or AST $>5 \times$ ULN for more than 2 weeks ALT or AST $>3 \times$ ULN and (total bilirubin $>2 \times$ ULN or INR >1.5) ALT or AST $>3 \times$ ULN with the appearance of fatigue, nausea, vomiting, right upper quadrant pain or tenderness, fever, rash, and/or eosinophilia ($> 5\%$), or jaundice 	
 Withhold study drug. Repeat LFTs within 48-72 hours. If LFTs confirmed, test for alternative cause(s) as described in Section 5.1.2.3. Monitor LFTs two to three times per week until decreasing or stabilized, then monitor LFTs weekly until AST and ALT are $\leq 5 \times$ ULN and total bilirubin is $\leq 2 \times$ ULN. Discontinuation of study drug should be considered. However, if event resolves to AST and ALT $\leq 5 \times$ ULN with total bilirubin $\leq 2 \times$ ULN, study drug may be resumed after consultation with the Medical Monitor. In general, re-initiation of study drug can be considered if there is clear evidence that the liver injury is not related to study drug or clearly attributable to other causes (as determined by the IMC), is showing signs of reversibility, and that the benefit-risk of continuing to receive study drug remains favorable (see Section 5.1.2.3). If a decision is made to permanently discontinue study drug, offer medical management per local standard of care and follow for safety.

ADA=anti-drug antibody; AESI=adverse event of special interest; LFT=liver function test; PK=pharmacokinetic; ULN=upper limit of normal.

Table 4 Guidelines for Management of Patients Who Experience Specific Adverse Events (cont.)

Event	Action to Be Taken
Thromboembolism or deep vein thrombosis	
Grade 1	
 Continue study drug and monitor closely for worsening of symptoms.
Grade 2 or 3	
 Treat as per local standard of care. Withhold study drug until the event resolves to a Grade 1 or lower. Report event to Sponsor in an expedited manner as an AESI (see Section 5.2.3).
Grade 4	
 Permanently discontinue study drug. Notify Medical Monitor and offer medical management per local standard of care, and follow for safety. Report event to Sponsor in an expedited manner as an AESI (see Section 5.2.3).
Efmarodocokin alfa-related adverse events not described above	
Grade 1 or 2	
 Continue study drug.
Grade 3	
 Withhold study drug. If event resolves to Grade 2 or better, resume study drug at the next scheduled dose. If more than one scheduled dose will be missed because of an on-going adverse event, permanently discontinue study drug.
Grade 4	
 Permanently discontinue study drug, offer medical management per local standard of care, and follow for safety.

ADA=anti-drug antibody; AESI=adverse event of special interest; LFT=liver function test; PK=pharmacokinetic; ULN=upper limit of normal.

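### Table 4 tells sites to restart drug when AST *or* ALT is back to ≤5× ULN, although either enzyme alone triggers the hold and monitoring runs until both have fallen

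*Combined protocol and SAP*

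**What the plan says.** Table 4 in Section 5.1.2.3 has three hepatic rows. The second applies when ALT or AST is >5× to ≤8× ULN. Drug is withheld, liver tests are repeated within 48–72 hours, and other causes are sought once the result is confirmed. The monitoring step reads "Monitor LFTs weekly until AST and ALT" are ≤5× ULN. The restart step reads "If event resolves to AST or ALT" ≤5× ULN "within 2 weeks after event onset, resume study drug". If that is not met, monitoring follows the third row.

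The third row has four triggers:
- ALT or AST >8× ULN
- ALT or AST >5× ULN for more than 2 weeks
- ALT or AST >3× ULN with bilirubin >2× ULN or INR >1.5
- ALT or AST >3× ULN with listed symptoms or jaundice

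Its restart sentence uses *and*: "However, if event resolves to AST and ALT" ≤5× ULN, with bilirubin ≤2× ULN. On stopping it says "Discontinuation of study drug should be considered", and it treats a permanent stop as a choice: "If a decision is made to permanently discontinue study drug, offer medical management per local standard of care".

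Section 4.6.1 lists severe liver injury by Hy's Law among the mandatory permanent stops. For Hy's Law, Sections 4.6.1, 5.1.2.3 (Hepatic Events) and 5.2.3 all point to Section 5.3.5.7. That section covers ECG findings; the liver section is 5.3.5.8.

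**The concern.** The second row is entered when *either* enzyme exceeds 5× ULN. The event is over only when *neither* does, which is what the monitoring sentence says. The restart sentence tests something weaker and can be satisfied by the enzyme that never triggered the hold. This is a direct dosing instruction to sites after liver injury, in a study whose main objective is safety and tolerability, so it should not rely on the reader to infer the intended word.

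Two smaller defects sit beside it. Someone following any of the three Hy's Law pointers lands in the ECG section. And no hepatic row of Table 4 repeats the mandatory stop from Section 4.6.1; Section 5.3.5.8 does not fill that gap, because it gives the definition and the reporting rule but no dosing action.

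**Working it through.** The plan gives no figure to reproduce. The check is a logic test of the wording and a timing bound.

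**1. Restart logic.** Inputs: the second-row trigger (ALT or AST >5× to ≤8× ULN) and the restart limit (≤5× ULN), both from Table 4.

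| ALT ≤5× ULN | AST ≤5× ULN | *or* met | *and* met |
|---|---|---|---|
| yes | yes | yes | yes |
| yes | no | yes | no |
| no | yes | yes | no |
| no | no | no | no |

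*Or* is met in 3 of 4 states and *and* in 1 of 4. In the two states where they differ, one enzyme is still above the limit.

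*Example A.* Trigger at ALT 7× and AST 6× ULN; within 2 weeks AST falls to 4× and ALT stays at 7×.
- *Or*: min(7, 4) = 4 ≤ 5, so restart is allowed.
- *And*: max(7, 4) = 7 > 5, so it is not.
- ALT stands at 7/5 = 1.4 times the limit.

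The remaining enzyme can be anywhere from just above 5× to 8× ULN, that is, up to 8/5 = 1.6 times the limit. Above 8× the third row takes over.

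*Example B.* Trigger at ALT 7× with AST 4× ULN. The *or* condition already holds at onset, so the restart line cancels the instruction to withhold.

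**2. Consistency of wording.** Four hepatic sentences set a monitoring or restart endpoint on the two enzymes. Three use *and* (second-row monitoring, third-row monitoring, third-row restart). One uses *or* (second-row restart).

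**3. Exposure.** Inputs: Q4W dosing with a ±5-day window (Appendix 1); the 2-week restart window (second row); the third-row trigger of >5× ULN for more than 2 weeks.
- Shortest interval between regular Q4W doses: 28 − 2 × 5 = 18 days.
- Restart window: 14 days. Since 18 > 14, at most one infusion can fall inside it.
- Appendix 1 schedules chemistry at the Q4W dosing visits. If the elevation is found on that sample and onset is dated to it, the next scheduled dose falls at least 18 − 14 = 4 days after the window closes. An enzyme still >5× ULN then meets the third-row trigger and drug is withheld, so the usual number of affected infusions is zero.
- The gap opens when the elevation is found on an off-schedule sample (for example at a disease evaluation visit, where Appendix 1 also lists chemistry) within 14 days before a dose, or when a withheld dose is given late.

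**4. Pointers.** Three Hy's Law references (Sections 4.6.1, 5.1.2.3 and 5.2.3) go to 5.3.5.7. The ECG reference to 5.3.5.7 in Section 4.5.7 is correct. The section numbering is therefore sound and only the three liver pointers need to change.

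**The case against.** The strongest reply is that nobody would apply the sentence literally. It speaks of the event resolving, it follows a sentence requiring both enzymes, and the literal reading defeats the row (Example B). The narrative in Section 5.1.2.3 adds that re-initiation recommendations for a given patient "are complex and require medical judgment (i.e., consultation between the investigator, medical monitor, and the IMC". All of this stands as evidence of intent and as a limit on harm. It does not make the restart line correct, and the line itself is an unqualified instruction to resume.

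Three stronger readings are tempting, and the documents do not support them.

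- *That Table 4 overrides the Hy's Law stop.* Section 4.6.1 is binding, while Table 4 is a set of guidelines. Section 5.3.5.8 defines Hy's Law injury as occurring without cholestasis or another cause of hyperbilirubinemia. The third row ties re-initiation, in general, to injury that is unrelated to drug or "clearly attributable to other causes (as determined by the IMC"). That row also covers several patterns that are not Hy's Law, for which considering discontinuation is reasonable. Most of the apparent conflict goes away; what is missing is a reminder line.
- *That Hy's Law is the only Section 4.6.1 stop without a Table 4 line or pointer.* Serious viral infection also lacks both. The pointer to Table 4 in that bullet concerns other infections, and Table 4's infection rows go by grade, with Grade 3 possibly resumed.
- *That the second row is deficient because its cell has no Medical Monitor step.* The Section 5.1.2.3 text covers re-initiation generally, and a lighter step for a lower tier is a design choice.

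**Conclusion.** The restart condition in the >5× to ≤8× ULN row is wrong as written and should be corrected. Its practical reach is small: usually no infusion and at most one, given with an enzyme between just above 5× and 8× ULN. That bound assumes regular Q4W dosing within ±5 days, onset dated to the sample that showed the elevation, and sites applying the third row once 2 weeks have passed. The one-off resumption after Week 52 (Section 3.1.3, Table 3) needs only 2 weeks since the last dose, so the 18-day figure does not cover it. The documents give no expected frequency of hepatic events, so the number of patients affected cannot be estimated.

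The three wrong pointers are certain but editorial. The absent Hy's Law line is a matter of clarity and does not amount to an established contradiction. Reporting within 24 hours and consultation with the Medical Monitor and the IMC limit harm throughout. No sample size, interval or analysis is affected.

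**What to change.** 1. In the >5× to ≤8× ULN row of Table 4, make the restart condition AST *and* ALT ≤5× ULN within 2 weeks of onset. This is the essential change and replaces one word.
2. Change the Hy's Law pointers in Sections 4.6.1, 5.1.2.3 and 5.2.3 from 5.3.5.7 to 5.3.5.8.
3. As a clarification, add to the third hepatic row: permanently discontinue if Hy's Law is confirmed (Sections 4.6.1 and 5.3.5.8). Correcting the pointers does not replace this line, since Section 5.3.5.8 says nothing about dosing.

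No new tests or visits are needed. The cost is a wording amendment, which under Section 9.6 needs IRB/EC approval and regulatory approval where locally required, and slightly less freedom to restart drug early.

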5.2 SAFETY PARAMETERS AND DEFINITIONS

Safety assessments will consist of monitoring and recording adverse events, including serious adverse events and adverse events of special interest, performing protocol-specified safety laboratory assessments, measuring protocol-specified vital signs, and conducting other protocol-specified tests that are deemed critical to the safety evaluation of the study.

Certain types of events require immediate reporting to the Sponsor, as outlined in Section 5.4.

5.2.1 Adverse Events

According to the ICH guideline for Good Clinical Practice, an adverse event is any untoward medical occurrence in a clinical investigation subject administered a pharmaceutical product, regardless of causal attribution. An adverse event can therefore be any of the following:

- Any unfavorable and unintended sign (including an abnormal laboratory finding), symptom, or disease temporally associated with the use of a medicinal product, whether or not considered related to the medicinal product
- Any new disease or exacerbation of an existing disease (a worsening in the character, frequency, or severity of a known condition) (see Sections [5.3.5.10](#) and [5.3.5.11](#) for more information)
- Recurrence of an intermittent medical condition (e.g., headache) not present at baseline (Study Week 0)
- Any deterioration in a laboratory value or other clinical test (e.g., ECG, X-ray) that is associated with symptoms or leads to a change in study treatment or concomitant treatment or discontinuation from study drug
- Adverse events that are related to a protocol-mandated intervention, including those that occur prior to assignment of study treatment (e.g., screening invasive procedures such as biopsies)

